11. Investigational agent or anticancer therapy (including chemotherapy, biologic therapy, immunotherapy, anticancer Chinese medicine, or other anticancer herbal remedy) within 5 half-lives or 4 weeks (whichever is shorter) prior to the first dose of study drug. In addition, no concurrent investigational anticancer therapy is permitted during the study.

12. Radiotherapy within 2 weeks of start of study treatment. Participants must have recovered from all radiation-related toxicities and not require corticosteroids.

13. Any unresolved toxicities from prior therapy greater than National Cancer Institute Common Terminology Criteria for Adverse Events (NCI-CTCAE) version 5.0 Grade 1 at the time of starting study drug with the exception of alopecia and Grade 2 platinum therapy-related neuropathy.

14. Use of sensitive substrates of major CYP450 isozymes.

Note: A list of substrates which are sensitive to these enzymes is provided in [Appendix B](#). If a sensitive substrate cannot be stopped and replaced with another medication, the patient's inclusion in the study should be discussed with the Sponsor.

15. Any illness, medical condition, organ system dysfunction, or social situation, including mental illness or substance abuse, deemed by the Investigator to be likely to interfere with a patient's ability to sign the ICF, adversely affect the patient's ability to cooperate and participate in the study, or compromise the interpretation of study results.

16. Received a live vaccine within 30 days of the first dose of study drug.

17. Active, uncontrolled systemic bacterial, viral, or fungal infection.

18. HIV-infected participants with a history of Kaposi sarcoma and/or Multicentric Castleman Disease.

19. Active infection as determined by hepatitis B surface antigen and hepatitis B core antibody, or hepatitis B virus deoxyribonucleic acid (DNA) by quantitative polymerase chain reaction (qPCR) testing.
20. Active infection as determined by hepatitis C virus (HCV) antibody or HCV RNA by qPCR testing.
21. Pregnant or lactating.
22. History of hypersensitivity to any of the study drug components.

[figure not shown]

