7.3.2. Cancer History

The following cancer history characteristics of solid tumor will be summarized descriptively (n, mean, Mean, Standard Deviation, Median, Min, Max) using the Safety Analysis Set:

- Time since date of initial histopathological diagnosis (months) = (date of first dose - date of initial histopathological diagnosis)/30.4375
- Time since date of most recent disease recurrence/progression (months) = (date of first dose - date of most recent disease recurrence/progression)/30.4375

The number and percentage of subjects with the following primary and metastatic cancer history for solid tumor will be summarized using the Safety Analysis Set:

QMS Document Name: Statistical Analysis Plan Template(EN)	Page 14 of 41
QMS No (include version ref): STF-015-GL.03	Document date: 14JUL2022
CONFIDENTIAL	

- Time since date of initial histopathological diagnosis (<12 months, >=12 months - < 24 months, >=24 months - < 36 months, >=36 months)
- Cancer type as recorded in eCRF
- Primary site of solid tumor as recorded in eCRF
- Any pathologic sub-type (Yes, No)
- Stage of solid tumor at initial diagnosis (0, I, II, III, IV)
- Stage of solid tumor at baseline (0, I, II, III, IV)
- Characterization of disease at study entry (locally advanced, metastatic)
- Metastatic site as recorded in eCRF
- Any known genetic mutations (Yes [BRAF, EGFR, HER2, KRAS, KIT, PDGFRA, PIK3CA, NRAS, VHL, Other], No)
- MSI status (Known [MSI-H, MSI-L, MSS dMMR, pMMR] Unknown, Not Applicable)
- TMB Status Known? (No, Not Applicable, Yes [High, Intermediate, Other])
- Tumoral genetic characterization (Yes, No, Not Applicable)

The following cancer history characteristics of lymphoma will be summarized descriptively (n, mean, Mean, Standard Deviation, Median, Min, Max) using the Safety Analysis Set:

- Time since date of diagnosis (months) = (date of first dose - date of initial diagnosis)/30.4375
- Time since date of transformation (months) = (date of first dose - date of transformation)/30.4375

The number and percentage of subjects with the following cancer history for lymphoma will be summarized using the Safety Analysis Set:

- Time since date of diagnosis (<12 months, >=12 months - < 24 months, >=24 months - < 36 months, >=36 months)
- Disease at screening as recorded in eCRF
- Current disease stage (I, IE, II, IIE, II BULKY, III, IV)
- Current Ann Arbor Staging (Stage I, Stage IE, Stage II, Stage IIE, Stage III, Stage IIIE, Stage IIIS, Stage IIIE/S, Stage IV, Not Applicable)

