7.3.3. Prior Cancer Therapy

Prior cancer therapy information will be summarized using descriptive statistics. Denominators for calculating percentages will be based on the number of subjects in the Safety Analysis Set. Summaries will include the following:

- Any prior anti-cancer therapy
- Type of prior anti-cancer therapy (Surgery, Radiation therapy, Systemic therapy)
- Type of Systemic Therapy (Chemotherapy, Immunotherapy, Hormonal therapy, Targeted therapy, Other)
- Systemic therapy setting (Advance/metastatic, Palliative, Other)
- Best overall response across all prior systemic therapies (CR, PR, SD, PD, NE, NA, Unknown)
- Best overall response from the latest prior systemic therapy (CR, PR, SD, PD, NE, NA, Unknown)
- Reason for stopping treatment in the latest prior systemic therapy (Treatment completed, Progressive disease, Toxicity, Adverse event, Other)
- Number of line of therapies (0, 1, 2, 3, ≥4)

QMS Document Name: Statistical Analysis Plan Template(EN)	Page 15 of 41
QMS No (include version ref): STF-015-GL.03	Document date: 14JUL2022
CONFIDENTIAL	

Time since the last prior systemic therapy started (months, date of first dose – start date of the last prior systemic therapy)/30.4375) will be descriptively (n, mean, Mean, Standard Deviation, Median, Min, Max) summarized using the Safety Analysis Set:

Prior systemic anti-cancer medications will be coded according to the latest version of World Health Organization drug dictionary (WHODRUG Global B3 March 2023) and stored with ATC categories and preferred names (PN). A primary ATC category will be selected before DBL based on considerations such as indication, route of administration, and dosage.

The number and percentage of subjects with medication use coded to each primary ATC level 2 category and preferred name (PN) combination will be summarized descriptively using the Safety Analysis Set. If a subject has received more than 1 drug within an ATC class or PN, the subject will be counted only once for this ATC class or PN.

Prior cancer therapy will be reported in data listings using the Safety Analysis Set.

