15.5. Appendix 5: Derived Data And Definitions

Derived Data And Definitions

Baseline & Change From Baseline

- The baseline is defined to be the last non-missing value prior to the first WTX-330 dose.
 - For assessments performed on Day 1, if the time of the day is missing but scheduled time point is recorded as pre-dose, the assessment may be considered the baseline assessment for the respective study procedures.
- Change from Baseline (CFB) = Post-baseline Assessment – Baseline Assessment.
 - CFB will be set to missing if corresponding post-baseline assessment or the baseline assessment is missing
- Percent CFB = $100 \times (CFB / \text{Baseline Assessment}) \%$, with the following exceptions:
 - If both CFB and baseline assessment are 0, the corresponding percent CFB will be set to 0.
 - If baseline assessment is 0 or missing but the CFB is non-zero, the percent CFB will be set to missing.

Age

Age at informed consent will be calculated from the date of birth to the date of informed consent.

Prior and Concomitant Medications, Procedures, and Medical Conditions

- Prior medications – all medications that ended before Day 1.
- Concomitant medications – all non-study drug medications used on/after day 1.
- Prior and concomitant procedures are defined analogously.

QMS Document Name: Statistical Analysis Plan Template(EN)	Page 37 of 41
QMS No (include version ref): STF-015-GL.03	Document date: 14JUL2022
CONFIDENTIAL	

Derived Data And Definitions

- If the start and/or end dates are partially recorded or missing completely, refer to Subsection 15.6 for the determination of prior vs concomitant status.

15.6. Appendix 6: Premature Withdrawals & Handling of Missing Data**Premature Withdrawals & Handling of Missing Data****Premature Withdrawals**

During the dose escalation phase, if a subject in Cycle 1 discontinues, holds, or modifies WTX-330 dose for a reason other than a DLT as reviewed by DEC and is not followed for safety for a minimum of 28 days, the subject may be replaced.

For the Dose Expansion Phase, subjects will be replaced if they do not have at least one post-baseline efficacy assessment and did not discontinue due to clinical progression.

Handling of Missing or Partial Dates

In the presence of missing or partial dates, the determination of “prior” and “concomitant” status for non-study drug medications, and TEAE will follow the rules below:

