Partial start date for Adverse Event, partial start date for Medications, and partial date of diagnosis

- if month and day are missing, and the year is the same as the year of first WTX-330 dose, then assign the date of first WTX-330 dose as start date; else assign Jan 1st of the year.
- if only the day is missing, and the month and year are same as the month and year of first WTX-330 dose, then assign the date of first WTX-330 dose as AE start date; else assign 1st day of the month.
- Compare the imputed date with the date of last known alive/contact; if the imputed date is later than the date of last known alive/contact, then assign the date of last known alive/contact as AE start date.

Partial end date for Adverse Event, and partial end date for Medications:

- Assign DEC 31st of the year if both Month and Day are missing.
- Assign last day of the month if only Day is missing.
- Assign ‘ongoing’ if Year, Month and Day are missing.
- Compare the imputed date with the date of last known alive/contact; if the imputed date is later than the date of last known alive/contact, then assign the date of last known alive/contact as AE end date.

The data listings will report original data instead of the imputed date. The imputed date will be used to categorized TEAE, Prior/Concomitant Medication.

QMS Document Name: Statistical Analysis Plan Template(EN)	Page 38 of 41
QMS No (include version ref): STF-015-GL.03	Document date: 14JUL2022
CONFIDENTIAL	

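### The partial-date rule in SAP 15.6 can turn an adverse event recorded as ended before dosing into a TEAE, and leaves unclear whether it also sets time since diagnosis

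*SAP*

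**What the plan says.** The lead-in to the missing-date rules in SAP 15.6 (Appendix 6) gives their purpose: "the determination of “prior” and “concomitant” status for non-study drug medications, and TEAE will follow the rules below". The start-date rule that follows is headed "Partial start date for Adverse Event, partial start date for Medications, and partial date of diagnosis", so three kinds of date share it.

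- Month and day missing: if "the year is the same as the year of first WTX-330 dose, then assign the date of first WTX-330 dose as start date"; otherwise 1 January of the recorded year.
- Only the day missing: if "the month and year are same as the month and year of first WTX-330 dose, then assign the date of first WTX-330 dose"; otherwise the first of the recorded month.
- One consistency check follows: "Compare the imputed date with the date of last known alive/contact". The imputed start is pulled back if it falls after that date. The event's own stop date is not mentioned.

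The last sentence of 15.6 says that imputed dates serve to classify TEAEs and prior or concomitant medications. It gives no other use.

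SAP 9.3.1.3 defines a TEAE by onset or worsening on or after first dose, up to 30 days after the last dose or the start of a new cancer regimen. It has no stop-date condition.

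SAP 7.3.2 defines "Time since date of initial histopathological diagnosis (months) = (date of first dose - date of initial histopathological diagnosis)/30.4375", with a matching formula for lymphoma. It reports the result both as a continuous variable and in the categories under 12, 12 to under 24, 24 to under 36, and 36 months or more.

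**The concern.** Moving an uncertain adverse-event start to the first dose is a sensible conservative default when the event might have begun on treatment. It is not conservative when the record already shows that the event ended before dosing. In that case the rule creates an impossible record and a false TEAE. TEAE frequency is a primary outcome of dose escalation (SAP 1.2), and escalation groups hold 3 to 6 patients (SAP 3.1). Because 15.6 has listings show the original dates, a reader of the listing would not see the start-after-stop conflict.

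The same default makes little sense for a diagnosis date. Entry requires an already confirmed relapsed or refractory diagnosis, so a diagnosis on the day of first dose is not credible. The same table also reports time since the most recent recurrence or progression, so a patient could appear to have progressed before being diagnosed.

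**Working it through.** The plan states no figure on this point, so there is none to reproduce. The check applies the 15.6 start rule literally to assumed dates, with months = days / 30.4375 as in SAP 7.3.2.

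**1. Adverse events.** Assumed: first dose 16 Oct 2023, last contact 1 Mar 2024.

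| Recorded start | Recorded stop | Imputed start | Start after stop? | TEAE? |
|---|---|---|---|---|
| 2023 | 9 Oct 2023 | 16 Oct 2023 | yes, by 7 days | yes |
| Oct 2023 | 9 Oct 2023 | 16 Oct 2023 | yes, by 7 days | yes |
| Sep 2023 | 9 Oct 2023 | 1 Sep 2023 | no | no |
| 2022 | 28 Dec 2022 | 1 Jan 2022 | no | no |

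The error arises only when the known part of the start matches the first-dose year (month and day missing) or month and year (day missing). One affected patient is 1/6 = 17% to 1/3 = 33% of a group of 6 or 3, in any table row where that patient has no genuine TEAE.

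**2. Diagnosis dates, if the rule feeds 7.3.2.** First dose again 16 Oct 2023.

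| True date | Recorded as | Imputed | Reported months | True months |
|---|---|---|---|---|
| 15 Mar 2023 | 2023 | 16 Oct 2023 | 0 / 30.4375 = 0.00 | 215 / 30.4375 = 7.06 |
| 2 Oct 2023 | Oct 2023 | 16 Oct 2023 | 0.00 | 14 / 30.4375 = 0.46 |
| 15 Mar 2023 | Mar 2023 | 1 Mar 2023 | 229 / 30.4375 = 7.52 | 7.06 |
| 20 Nov 2022 | 2022 | 1 Jan 2022 | 653 / 30.4375 = 21.45 | 330 / 30.4375 = 10.84 |
| 15 Jun 2019 | 2019 | 1 Jan 2019 | 57.46 | 52.04 |

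**3. Bounds.**
- Same-year, year-only date: understated by at most 364 / 30.4375 = 11.96 months. Every same-year gap is at most 364 days, below 12 months, so the lowest category stays correct. Only the mean, median and minimum can move.
- Matching month, day missing: understated by at most 30 / 30.4375 = 0.99 months.
- Earlier year-only date: never understated, and overstated by at most 364 / 30.4375 = 11.96 months.

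**4. Category shift for earlier year-only dates.** Take a diagnosis recorded as 2022 and a first dose on 15 Mar 2023. The imputed gap is 438 days, and 438 / 30.4375 = 14.4 months, so the patient is placed in 12 to under 24. The true gap lies between 74 and 438 days. If all 365 dates in 2022 are equally likely, the mean is (74 + 438) / 2 = 256 days, or 8.4 months. Gaps of 74 to 365 days, which is 292 dates, fall under 12 months: 292 / 365 = 80%.

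The share depends on the dosing date. With first dose on day d of 2023 (d from 2 to 365) it is (366 − d) / 365. For 16 Oct (d = 289) it is 77 / 365 = 21%. The full range is 364 / 365 = 99.7% down to 1 / 365 = 0.3%.

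**5. Heading against closing sentence.** A diagnosis date has no role in TEAE or medication status. Its evident use is time since diagnosis. So either the rule feeds 7.3.2 with the results above, or the reference to diagnosis in the heading has no effect and partial diagnosis dates have no stated rule.

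**The case against.** The strongest reply is that the text already points away from the error. SAP 15.4 treats screening-period events as pre-treatment unless otherwise specified, and 9.3.1.3 requires emergence or worsening on or after first dose. The case is also narrow: screening starts no earlier than Day −28 (15.4), and clinically significant examination findings at screening go to medical history (9.8). The narrowness stands. The rest does not remove the problem, because 15.6 specifies that the imputed date decides TEAE status, and a program written to it returns a TEAE.

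On diagnosis, the closing sentence of 15.6 leaves out time since diagnosis, and 7.3.2 does not refer to 15.6. That is a fair objection to saying that patients will be reported at 0 months. What remains is a contradiction to resolve, with a conditional consequence.

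Three stronger readings are tempting, and the documents do not support them.

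- A reader might infer that the rule also sets the interval "Time since the last prior systemic therapy started (months, date of first dose" in 7.3.3 to zero. Section 15.6 does not name prior anticancer therapy, and 7.3.3 does not refer to it. The reference to 15.6 from the analysis sections is in 7.4.1, under non-cancer and concomitant therapies.
- A reader might argue that 0 months is impossible because every patient must have had prior therapy and a washout. Inclusion criteria 2 and 3 also admit patients with no standard therapy of proven benefit, and 7.3.3 tabulates 0 prior lines. Exclusion criterion 11 bars treatment "within 5 half-lives or 4 weeks (whichever is shorter) prior to the first dose of study drug"; it does not require earlier treatment.
- A reader might expect medication status to be distorted too. Prior status depends on the end date (7.4.1 and 15.5), so an imputed start does not change it.

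**Conclusion.** The adverse-event part holds as written. When a partial start matches first dose and the recorded stop precedes it, 15.6 with 9.3.1.3 yields a false TEAE that starts after it ends.

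The diagnosis part holds conditionally. If the rule feeds 7.3.2, matching partial dates give exactly 0 months with the category unaffected. Earlier year-only dates are overstated by 0 to 11.96 months and can move up a category. Whether it feeds 7.3.2 is unclear because heading and closing sentence disagree.

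The example dates are assumptions, and the 80% and 21% shares also assume true dates spread evenly over the year. The documents do not give the number of partial dates, so the effect on any table cannot be sized. This is a minor point, with the adverse-event limb the more consequential.

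**What to change.** 1. Add to the adverse-event start rule in 15.6: unless the recorded or imputed stop date is before first WTX-330 dose, in which case the imputed start is set no later than the stop date and the event is not a TEAE. Using the imputed stop is safe because 15.6 sets a partial stop to the last day of the known month or year. If even that day precedes first dose, the event had ended.

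2. Take diagnosis dates out of this rule. Impute them at the midpoint of the possible interval: the known year or month, truncated at the day before first dose or, if sooner, at the earliest documented later progression or therapy date. State that these dates feed the 7.3.2 intervals, and amend the closing sentence of 15.6 to match.

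Truncating before taking the midpoint matters. For a diagnosis recorded as 2023 and first dose on 15 Mar 2023 (day 74), the possible days are 1 to 73 and the midpoint is day 37. The interval is then 37 / 30.4375 = 1.22 months. A fixed 1 July capped at the day before dosing would give 1 / 30.4375 = 0.03 months, close to the zero it is meant to avoid. For a diagnosis recorded as 2022 with the same first dose, the midpoint rule gives 256 / 30.4375 = 8.4 months instead of 14.4.

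The cost is a few SAP sentences and a small programming change. No data collection or trial conduct is affected.

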15.7. Appendix 7: List of Abbreviations

Abbreviation	Description
ADA	Anti-drug antibody
ADaM	Analysis Data Model
AE	Adverse event
AESI	Adverse event of special interest
ALT	Alanine aminotransferase
ALP	Alkaline phosphatase
AST	Aspartate aminotransferase
ATC	Anatomical Therapeutic Chemical
BOR	Best overall response
CD	Cluster of differentiation
CFB	Change from baseline
CI	Confidence interval
COVID-19	Coronavirus Disease 2019
CR	Complete response
CRP	C-reactive protein
CRS	Cytokine release syndrome
CSR	Clinical Study Report
DLT	Dose-limiting toxicity
dMMR	Deficient mismatch repair
DoR	Duration of response
ECG	Electrocardiogram
ECOG	Eastern Cooperative Oncology Group
eCRF	Electronic Case Report Form
eGFR	Estimated glomerular filtration rate
EoT	End of Treatment
iBOR	Immune-best overall response
iCBR	Immune-clinical benefit rate
ICH	International Council for Harmonisation
IL	Interleukin
iCPD	Immune-confirmed progressive disease

QMS Document Name: Statistical Analysis Plan Template(EN)	Page 39 of 41
QMS No (include version ref): STF-015-GL.03	Document date: 14JUL2022
CONFIDENTIAL	

Abbreviation	Description
iCR	Immune-complete response
iDoR	Immune-duration of response
IFN	Interferon
IL	Interleukin
IL-2R	Interleukin-2 receptor
iORR	Immune-overall response rate
iPFS	Immune-progression-free survival
iPR	Immune-partial response
iRECIST	Immune-Response Evaluation Criteria in Solid Tumors
iSD	Immune-stable disease
iUPD	Immune-unconfirmed progressive disease
LDH	Lactic acid dehydrogenase
Max.	Maximum
MedDRA	Medical Dictionary for Regulatory Activities
Min.	Minimum
MMR	Mismatch repair
mRCC	Metastatic renal cell carcinoma
MSI	Microsatellite instability
MSI-H	MSI-High
MSI-L	MSI-Low
MSS	Microsatellite stable
MTD	Maximum tolerated dose
NCI-CTCAE	National Cancer Institute Common Terminology Criteria for Adverse Events
NE	Not evaluable
NK (cells)	Natural killer (cells)
ORR	Overall response rate
OS	Overall survival
PD	Progressive disease
PFS	Progression-free survival
PK	Pharmacokinetic(s)
pMMR	Proficient mismatch repair

QMS Document Name: Statistical Analysis Plan Template(EN)	Page 40 of 41
QMS No (include version ref): STF-015-GL.03	Document date: 14JUL2022
CONFIDENTIAL	

Abbreviation	Description
PN	Preferred name
PR (except for PR interval)	Partial response
PT	Preferred term
PTT	Partial thromboplastin time
QTc	QT interval corrected for heart rate
QTcF	QT interval corrected for heart rate using Fridericia's formula
RECIST	Response Evaluation Criteria in Solid Tumors
SAE	Serious adverse events
SAP	Statistical Analysis Plan
SD	Stable disease
SOC	System organ class
StdDev	Standard deviation
TEAE	Treatment-emergent adverse event
TNF	Tumor necrosis factor
TTE	Time to event
ULN	Upper limit of normal
WHODrug	World Health Organization Drug Dictionary

Werewolf Therapeutics, Inc.

A Phase 1 (First-In-Human [FIH]), Multi-Site, Dose Escalation and Expansion Study of WTX-330 in Adult Patients with Advanced or Metastatic Solid Tumors or Lymphoma

TFL Shells

Author: [name]

SAP Version: 2.0

Table Shell Version: 2.0

Caidya Code: WWT21330

Table of Contents

Approval and Signature Page.....	3
Format and Ordering of Treatment Groups.....	4
General Display Conventions.....	4
Sorting Conventions.....	5
Display of Continuous Statistics	5
Display of Percentages	5
Display of P-Values	5
Display of Dates in Subject Data Listings.....	6
Display of Missing Values in Subject Data Listings.....	6
Modification History	6
List of Tables.....	7
List of Figures	13
List of Listings	14
Table Shells	16
Figure Shells.....	90
Listing Shells.....	95

[figure not shown]
Approval and Signature Page

Approved by:

Name, Institution, and Job Title	Signature	Date
[name] Senior Manager Biostatistics Caidya	
Signed by:   Signer Name: [name] Signing Reason: I am the author of this document Signing Time: 26-Feb-2025 7:28:54 PM GMT 3F1277AD321D4048BF564AE5BED08E47
	26-Feb-2025
[name] Biostatistician Werewolf Therapeutics, Inc.	
Signiert von:   Name des Unterzeichners: [name] Signiergrund: Ich genehmige dieses Dokument Signierzeit: 26-Feb-2025 7:59:53 PM GMT 988B94B1FDA24A35AEB8361DCA46EBF3
	26-Feb-2025

Format and Ordering of Treatment Groups

The study includes Dose Escalation and Dose Expansion as the strategy below.

CPI = checkpoint inhibitor; MTD = maximum tolerated dose; Q2W = every 2 weeks; r/r = relapsed/refractory; SOC = standard of care.

Disposition, demographic, baseline characteristics, disease history, efficacy, and safety summaries will be presented as follows.

Dose Escalation will be presented by dose level – **additional columns will be added if more dose levels/schedules are tested:**

WTX-330	Total							
0.016	0.032	0.056	0.084	0.126	0.190	0.290	0.XXX	
mg/kg								

Dose Expansion will be presented by Arm:

Arm A	Arm B	Total
Note: Arm A = Patients with indications for which a CPI is indicated/approved; Arm B = Patients with tumor types for which CPI therapy is not indicated/approved.		

Overall response rate (ORR) and immune-overall response rate (iORR) in Dose Expansion will be further summarized by indication

Arm A				Arm B			
RCC	NSCLC	HNSCC	XXXXXX	CC	FL	DLBCL	YYYYYY

Note: Arm A = Patients with indications for which a CPI is indicated/approved; Arm B = Patients with tumor types for which CPI therapy is not indicated/approved.

Note: RCC = Renal Cell Carcinoma; NSCLC = Non-small Cell Lung Cancer; HNSCC = Head and Neck Squamous Cell Carcinoma; XXXXXX = █; CC = Colorectal Carcinoma; FL = Follicular Lymphoma; DLBCL = Diffuse Large B-cell Lymphoma; YYYYYY = █.

Column headers will be updated according to the indication in Arm A and B.

General Display Conventions

Summary tables and subject data listings will be in landscape format. Table titles will be centered.

Sorting Conventions

For AE and MH summaries, Primary SOCs and PTs will be ordered by descending count in overall Total (last column in table display). Other summaries will follow table shells layout.

Display of Continuous Statistics

Means and medians will be shown to one more decimal place, and the standard deviation will be shown to two more decimal places than the source data values. In cases where variables are derived and have floating point values (no fixed number of decimal places), an appropriate level of precision will be determined based on the context.

Statistics that cannot be derived will be shown as a dash (“-”) in summary tables.

Two-Sided confidence intervals are displayed with a format such as “(xx.x, xx.x).” If a confidence interval cannot be produced due to insufficient data, then a dash (“-”) will be shown in place of the entire confidence interval.

Display of Percentages

The following conventions apply for percentages:

- Percentages will be displayed to one decimal place unless otherwise specified
- No percentage will be shown if the corresponding count is 0
- Percentages that are exactly equal to 100% will be displayed as “100%”
- Percentages that round down to 0.0% will be displayed as “<0.1%”
- Percentages that round up to 100.0% will be displayed as “>99.9%”

Percentages are shown in parentheses after the corresponding count such as “25 (5.2%)” where extra spaces are included after the left parenthesis to ensure that decimal places for all percentages align within the same column.

Display of P-Values

Unless otherwise noted, p-values will be displayed as follows:

- P-values between 0.0001 and 0.9999 will be displayed in the format “0.xxxx”
- P-values that are exactly equal to 1 will be displayed as “1.0000”
- P-values <0.0001 will be displayed as “<0.0001”
- P-values >0.9999 and not exactly equal to 1 will be displayed as “>0.9999”

P-values that are descriptive and not associated with a formal test of hypothesis will not be flagged based on statistical significance. The following note will be shown in the table:

Note: P-values are for descriptive purposes and are not evaluated for statistical significance.

Unless otherwise noted, p-values that are statistically significant will be flagged with an asterisk. The table footnote is dependent on the setting, but the following example footnote is appropriate for many settings:

* Statistically significant at the 0.05 level.

Display of Dates in Subject Data Listings

Dates will be shown in one of the following formats:

- YYYYMMDD for complete dates
- YYYYMM for dates with only a month and year
- YYYY for dates with only a year

Partial dates are not imputed for subject data listings even if such dates are imputed for statistical algorithms. Relative day (if shown) is only derived for complete dates.

Dates will be shown in ISO8601 format as follows:

- DDMMYYYY for complete dates
- MMMYYYY for dates with only a month and year
- YYYY for dates with only a year

Partial dates are not imputed for subject data listings even if such dates are imputed for statistical algorithms. Relative day (if shown) is only derived for complete dates.

Display of Missing Values in Subject Data Listings

For subject data listings, missing numeric values will be shown as a dash (“-”). Missing character values will be shown as blanks.

Modification History

Version	Date	Author	Changes from Previous Version
0.1	19Dec2023	[name]	N/A – First Version
0.2	12Jun2024	[name]	Add shift tables for Deauville Scale
0.3	21Jun2024	[name]	Update footnote in TEAE table based on Werewolf's comments, correct typos
1.0	21Jun2024	[name]	Accept changes in version 0.3
1.1	18Feb2025	[name]	Correct Typo Select the TFLs for aCSR based on WW request
1.2	25Feb2025	[name]	Correct Typo Add TFLs for free IL-12 PK summary
2.0	26Feb2025	[name]	Accept changes/WW edits in draft 1.2

List of Tables

14.1 Study Population and Baseline.....	17
